3. BACKGROUND AND RATIONALE

Pulmonary Arterial Hypertension (PAH) is a progressive illness that; if not diagnosed early or left untreated, can be a severe life limiting condition (1). It is a chronic disease of the pulmonary vasculature, with vascular proliferation and remodelling of the small pulmonary arteries leading to a progressive increase in pulmonary vascular resistance (PVR). This can ultimately lead to right heart failure and premature death (2). The predominant symptom of PAH is dyspnoea on exertion, with a decrease in exercise capacity, and most patients present with this symptom (2).

PAH is an uncommon condition, affecting about 6000 patients in the United Kingdom (3), and due to its rarity, the NHS commissions 7 centres to care for patients with PAH (4). Oxford University Hospital works closely with the Royal Brompton Hospital to provide care for patients with PAH in Oxfordshire and the surrounding region.

The six-minute walk test (6MWT) is a standard method for measuring exercise capacity in patients with cardiopulmonary disease such as PAH. The 6MWT measures how far a patient can walk in 6 minutes. Walking is an activity performed every day, by most patients except for those most severely limited. By assessing patients' ability to exercise, the 6MWT provides a global assessment of respiratory, cardiovascular, neuromuscular and cognitive function. The 6MWT does not differentiate what limits the patient, nor does it assess maximal exercise capacity. Instead, the 6MWT allows the patient to exercise at a daily functional level, and is a useful tool for assessing changes after a therapeutic intervention, and correlates with a subjective improvement in dyspnoea (5).

In PAH the 6MWT is used to evaluate patients' response to treatment, with an increase in 6MWT distance of greater than 42 m being considered a clinically significant improvement (6). Furthermore,

Principal Investigator:

[name]

Short Title:

6-APP Study

Ethics Ref:

insert

change in 6MWT distance correlates with VO2 max, NYHA class and mortality in PAH patients, (7) providing an objective assessment of disease progression, prognosis and response to treatment. It is a universally accepted test as it is safe and easily performed by the patient.

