The 6MWT has become the primary end-point for many trials, and as a surrogate invalidated survival outcome for all placebo controlled trials of PAH therapy (8). It is used by regulatory bodies to determine whether a treatment should be approved. However, there is much discrepancy between whether it is the total distance walked at baseline prior to treatment, a decrease in total distance walked over time or a percentage increase in walking distance that correlates best with survival outcome. We hypothesize that it is all 3 of these measures, and that having a validated and more reproducible 6MWT would help assess patients and guide treatment strategies better.

The test is usually performed in hospital, by walking along a hospital corridor, where many factors on the day of the test can affect patients' performance, including tiredness, unfamiliarity with the environment or anxiety. The test typically requires 2 physiologists to monitor the distance walked by the patient, their oxygen saturations by pulse oximetry, and to record symptoms felt during the test. To improve the assessment of a patient's exercise capacity using a 6MWT, we hypothesized that the test would reflect more the patient's functional status, if it were undertaken prior to the hospital outpatient appointment. We have designed a mobile-phone "app" that allows patients to perform the 6MWT within the patient's home environment. This is felt to be more appealing to the patients, and would reduce the time spent in hospital on the day of their outpatient appointment.

The 6MWT app is categorised as mobile-health (m-health) system, a form of telehealth whereby healthcare is delivered at a distance using smartphones. By utilizing biometric collection devices such as a pulse oximeter monitor with Bluetooth capability, m-health can be used to measure the oxygen saturation levels in the blood from patients, and transmit them to a secure server, allowing them to be reviewed by cardiologists and other healthcare professionals.

The evidence-base for m-health as a tool for assessing physical fitness is increasingly established (9, 10). This new approach not only offers the opportunity for reliable collection of data, but provides the infrastructure to do this at scale and will allow decisions on patient's health to be based on more frequent and more accurate information.

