There are no known risks to undertaking a 6MWT in the community as walking is an activity of daily living, and all patients are encouraged to walk daily.

The population to be studied would be those with PAH who are currently assessed with a 6MWT. Once the app has been validated, patients with any type of cardiorespiratory disease who are assessed with a 6MWT could use the app, for example patients with chronic obstructive airways disease, heart failure, renal failure, pre-transplantation work up.

The 6MWT results form part of the NHS data set collected by NHS England for patients with PAH, and it would be beneficial to have a more reproducible assessment, whose results can be compared between the 7 centres providing care for these patients. At present, there is much variability in how 6MWTs are performed between units, and the app would reduce this variability.

Principal Investigator:

[name]

Short Title:

6-APP Study

Ethics Ref:

insert

The 6MWT has been undertaken at the JR for 5 years and we would like to retrospectively analyse the data from the 6MWT that have previously been undertaken. The data on patients will be pseudo-anonymised, i.e. no personal information like name, surname or address, will be used, but we will keep date of birth, gender, diagnosis, dates and results of the 6MWT, date and causes of death. As part of the clinical care team reviewing the data is part of the normal standard of care for patients with PHT. The data is collected on the Solus cardiac reporting system and can be extracted from this database and the data will be pseudo-anonymised by the PI for analysis, and then shared with the wider research team. The data would be analysed to look at distance walked, and change in Oxygen saturation and heart rate during the test. We would analyse the data over time, to look for changes in these parameters and correlate these with outcome data, ie mortality. The data would be anonymised when reviewed.

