5. STUDY DESIGN

We propose to evaluate a novel approach to service delivery by monitoring PAH patients using an established m-health system to send 6MWT results to a central server where they can be accessed by the clinical team (Figure 1). The system includes a mobile phone “app” to allow participants to comfortably perform the 6MWT at home (indoors or outdoors). In the outdoor scenario, the app makes use of GPS to track the user’s position. In the indoor scenario it uses the phone’s accelerometer and magnetometer (compass) to count the number of laps over a fixed-length walkway.

[figure not shown]
Figure 1. Diagram of the system

Principal Investigator:
Short Title:

[name]
6-APP Study

Ethics Ref:

insert

Undertaking a 6MWT test within the participant's home environment, using mobile technology to transmit the results via a software application on a mobile phone is appealing as it is likely to be more acceptable to the participant, may provide more consistent and functionally relevant data, and may reduce hospital attendances and healthcare costs. By utilizing biometric collection devices such as a pulse oximeter monitor with Bluetooth capability, telehealth can be used to capture the oxygen saturation levels in the blood from participants and transmit them to a secure server, allowing them to be reviewed by cardiologists and other healthcare professionals.

This study aims to compare the indoor 6MWT, with the hospital performed 6MWT. It will assess the feasibility and acceptance of a mobile phone app as an instrument to measure the 6MWT.

The 6MWT is currently undertaken at every Outpatient appointment, normally at 0- 3-, 6- and 12-month outpatient reviews. The participant would perform a hospital based 6MWT, whilst simultaneously using the indoor version of the app on their own mobile phone at baseline, 3- and 6-month follow up. This will demonstrate to the participant how to use the app, and we will be able to understand whether they are able to use it correctly. It will also allow direct comparison of the standard 6MWT distance measurement with the measurement provided by the app.

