The participant will be then invited to use the app in their local environment, preferably in the outdoor scenario, and the collected information would then be transmitted to the hospital servers where it could be reviewed. The app could be used many times prior to attendance in outpatients, giving the clinicians more detailed information as to the overall functional status of the patient. Participants will be required to perform a test before and after their follow up appointments so that home-based measurements can be compared to hospital-based ones. They will be allowed to do as many tests as they are willing to, preferably once per week and at least each month.

Principal Investigator:

[name]

Short Title:

6-APP Study

Ethics Ref:

insert

In total, we aim to collect 3 indoor hospital-based measurements (baseline, 3- and 6-month) and at least 5 outdoor home measurements, one close to each hospital visit plus one between two visits. The data collected will allow us to understand the usage of the app by participants, validate the indoor measurements and correlate the home measurements with the hospital-based ones.

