10.3. Analysis of Outcome Measures

All participants' data will be used excluding those who withdrew consent.

Primary Objective:

Principal Investigator:	[name]	Ethics Ref:	insert
Short Title:	6-APP Study		

O1: We will measure the percentage of participants who perform at least one home 6MWT between baseline visit and 3-month visit and the percentage of participants who perform at least one home 6MWT between baseline visit and 6-month visit. These two percentages will be used as the main measure of the success of this study.

In addition, the distribution over time of when home performed tests will be computed.

Secondary Objectives

O2: We will compute the mean and standard deviation of the difference in distance as measured by the physiologists and the app. To evaluate the agreement between the two approaches, a Bland Altman graph will be also prepared.

O3: We will compute the correlation of the distance as computed by the app when used at home within 3 days from the hospital visit with the one gathered in the hospital 6MWT test.

O4: Ease of use, acceptance and mobile phone affinity will be measured with standard questionnaires. Compliance with the use of the app will be measured by counting the frequency of use of the app. Simple descriptive statistics will be computed and correlations among quantities will be explored. A selected number of participants will be chosen for semi-structured interviews in order to gain a deeper understanding of their usage of the app.

Tertiary Objectives

O5: Descriptive statistics about the walked distance, blood oxygen saturation and heart rate, BORG scale and number of steps will be used to compare changes before and after initiation of new therapies.

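### Section 10.3 plans no estimate of within-participant variability of home 6MWT distance, so O5 has no noise term, the O3 correlation has no known ceiling, and the 42 m threshold cannot be applied to home tests

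*Combined protocol and SAP*

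**What the plan says.** **Home tests collected.** Section 5 asks for home tests "preferably once per week and at least each month" and aims for "at least 5 outdoor home measurements, one close to each hospital visit plus one between two visits". Sections 7.4 and 7.5 repeat the weekly or monthly request. Home tests may be indoor or outdoor, with outdoor preferred.

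**How Section 10.3 uses them.**
- O1: whether a participant did at least one home test by 3 and by 6 months, and when tests were done.
- O3: correlation of home with hospital distance, for home tests "when used at home within 3 days from the hospital visit". Section 4 instead pairs each visit with the following or nearest home test and gives no window.
- O4: frequency of app use.
- O5: descriptive statistics, including distance, before and after a new therapy, without saying which tests count.

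O2 and its Bland-Altman graph compare app and physiologist on one simultaneous hospital walk in indoor mode.

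**What the results are meant to inform.** Section 3 describes "an increase in 6MWT distance of greater than 42 m being considered a clinically significant improvement" and hypothesises that "having a validated and more reproducible 6MWT would help assess patients and guide treatment strategies better". Section 5 says that home testing "may provide more consistent and functionally relevant data". The O5 objective in Section 4 asks whether the app detects changes in distance better than the hospital test in patients starting advanced therapies.

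**The concern.** Whether an instrument can detect change depends on how far its readings vary in a participant who has not changed. Neither the methods list in Section 10.1 nor the analyses in Section 10.3 include a quantity that measures this for home distance, and Section 10 never refers to 42 m. Three things follow.

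- **O5.** A before/after difference cannot be judged without the test-to-test noise it must exceed.
- **O3.** The home-hospital correlation is limited by the repeatability of both tests. With that unknown, a modest value is hard to read, and a high value does not show that individual changes can be detected.
- **The 42 m threshold.** Section 8.2 judges device error against clinical relevance, but device error is only part of the variation between two home walks.

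O2 cannot fill the gap. Two readings of the same walk show measurement agreement, not test-retest variation, and not in outdoor mode.

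**Working it through.** The documents state no repeatability, power or sample-size figure, so there is nothing to reproduce.

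**Inputs from the documents:** 42 m (Section 3); 30 participants (Section 10.2); at least 5 home tests (Section 5); monthly or weekly testing over 6 months, so about 6 or 26 tests; average app error 5.58 m indoors (absolute) and 11.23 m outdoors (Section 8.2).

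**Assumed:** the within-participant SD, Sw, over a range; the between-participant SD in step 3.

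**1. Change that two single tests can show.** Repeatability coefficient = 1.96 × √2 × Sw = 2.77 × Sw. Setting this to 42 m gives Sw = 42 / 2.77 = 15.2 m.

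| Assumed Sw (m) | One test v one test (m) | Mean of 4 v mean of 4 (m) |
|---|---|---|
| 10 | 27.7 | 13.9 |
| 15 | 41.6 | 20.8 |
| 20 | 55.4 | 27.7 |
| 25 | 69.3 | 34.6 |
| 30 | 83.2 | 41.6 |

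The last column divides by √4 = 2 and assumes independent tests.

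**2. What Section 8.2 suggests.** If the error is normal with mean zero, and the outdoor average is also an absolute error (both assumptions), SD = average error × √(π/2).
- Indoor: 5.58 × 1.253 = 7.0 m, coefficient 19.4 m.
- Outdoor: 11.23 × 1.253 = 14.1 m, coefficient 39.0 m.

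Outdoors this leaves √(15.15² − 14.07²) = 5.6 m of SD for everything else before 42 m is exceeded. Any constant bias within the 11.23 m would cancel in a change and relax this limit.

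**3. Why the O3 correlation does not settle it.** With between-participant SD Sb and equal Sw in both tests, the expected correlation is r = Sb² / (Sb² + Sw²). For an assumed Sb of 100 m:
- Sw 15 m: 10,000 / 10,225 = 0.98, coefficient 41.6 m.
- Sw 25 m: 10,000 / 10,625 = 0.94, coefficient 69.3 m.
- Sw 40 m: 10,000 / 11,600 = 0.86, coefficient 110.9 m.

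At Sw 25 m, r is 0.91 for Sb 80 m and 0.96 for Sb 120 m. A high correlation is compatible with a coefficient well above 42 m.

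**4. Whether the data can estimate Sw.** With n participants and m tests each, df = n(m − 1), and the 95% limits are Sw × √(df / χ²).

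| n | Tests each | df | Limits (× Sw) |
|---|---|---|---|
| 30 | 5 | 120 | 0.89 to 1.15 |
| 30 | 6 | 150 | 0.90 to 1.13 |
| 30 | 26 | 750 | 0.95 to 1.05 |
| 15 | 5 | 60 | 0.85 to 1.22 |

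The rows for 30 are a best case: everyone contributes every test in one mode, none is excluded, and no participant-specific slopes are fitted. With such slopes, 6 tests each leave 30 × (6 − 2) = 120 df.

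**5. The hospital walks.** There are three per participant, about 3 months apart. With participant slopes, df = 30 × (3 − 2) = 30 at most, with limits 0.80 to 1.34. Without them, true individual change over 6 months is counted as error.

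**The case against.** The study is exploratory, its main measure of success is uptake, and no numbered objective asks for repeatability. O5 is tertiary and descriptive. The analysis could also be added later from the same data. All of this stands. It makes the gap a missed analysis, not a flaw in the primary endpoint. It does not remove the gap, because O5's own question concerns detection of change and O3 needs the same quantity to be read.

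A reader might infer more than the documents support:

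- **That home tests outside the 3-day windows go unused.** They enter O1 and O4 as timing and counts, and may enter O5 as distances. What is missing is their use for repeatability, and tests inside the windows are not used for that either.
- **That reproducibility is why the app was built.** Sections 3 and 5 also give functional relevance, patient appeal, time in hospital, attendances and cost. The remark that "the app would reduce this variability" concerns differences between units in how the test is performed; a within-participant SD would not address those.
- **That a within-participant SD would explain a low O3 correlation.** It pools app error, route and day-to-day variation. O2 informs app error in indoor mode only.
- **That the added analysis would show the home test to be more reproducible than the hospital test.** Three hospital walks 3 months apart are not a like-for-like comparator.
- **That home tests cannot show 42 m.** The 15.2 m limit applies to one test against one test, and Section 5 foresees many tests before a clinic visit.

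**Conclusion.** The concern holds as a gap in the written analysis plan. Repeated home distances will be collected, but no within-participant variability is to be estimated. As planned, O5 has no noise term, O3 has no known ceiling, and no statement about 42 m can be made for a home test.

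The size of the problem is unknown because Sw is not in the documents. A single pair of tests suffices only if Sw is about 15.2 m or less; with means of four independent tests the limit doubles to about 30.3 m. The 20 m and 30 m values are illustrations, not estimates. The outdoor error in Section 8.2, under the assumptions stated, comes close to the single-test limit before the participant's own variation is added, so the question is open.

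The data should answer it usefully even with partial uptake: 15 participants with 5 tests each still give limits of 0.85 to 1.22. The change is worth making; the primary objective does not depend on it.

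**What to change.** Add to Section 10.3, under O3:

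- Fit a mixed model to all home distances, outdoor and indoor modes separately, with a participant intercept and a time trend, excluding tests after a new therapy starts.
- Report the within-participant SD with its 95% CI, the repeatability coefficient (2.77 × SD) and the ICC, with the numbers of participants and tests behind them.
- Set the coefficient against 42 m, for single tests and for means of several tests.
- Use the SD when interpreting O3 and O5.
- State that this SD combines app error, route and day-to-day variation without separating them, and that O2 informs app error in indoor mode only.
- Report any SD from the hospital walks as descriptive only, and say that it mixes true change with error and does not by itself support a claim of better reproducibility than the hospital test.

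The cost is one extra analysis. No new visit, procedure or data collection is needed.

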4. OBJECTIVES AND OUTCOME MEASURES

Objectives	Outcome Measures	Timepoint(s) of evaluation of this outcome measure (if applicable)
Primary Objective O1: To demonstrate that patients are able and willing to use the app for the 6MWT	Percentage of participants who perform app-based home 6MWT	TP 1: 3 months after baseline visit TP 2: 6 months after baseline visit
Secondary Objectives O2: To validate app 6MWT measurements against the hospital 6MWT. O3: To compare the outdoor 6MWT app with the hospital based 6MWT.	Average and variability of the difference in distance as measured by physiologists and the app. Correlation of outdoor 6MWT app parameters with the hospital 6MWT test.	TP 1: at baseline visit TP 2: at 3-month visit TP 3: at 6-month visit TP 1: baseline visit 6MWT compared with following home test TP 2: 3-month visit 6MWT compared with closer home test before or after TP 3: 6-month visit 6MWT compared with closer home test before or after

Principal Investigator:

[name]

Short Title:

6-APP Study

Ethics Ref:

insert

O4: To assess the usability and acceptance of the app and the physicians' website.	Standard usability and acceptance questionnaire to users assessing their use of the app and website, semi structured interviews, analysis of technical logs.	TP 1: at 6 months after baseline visit
Tertiary Objectives	O5: To test whether the 6MWT app can detect changes in 6MWT distance more effectively than the hospital 6MWT, in patients starting advanced therapies.	Comparison of change in 6MWT app measurement with hospital 6MWT measurement, measured before and after initiation of new therapies.

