7.5. Subsequent Visits

The participants will be followed up as per the normal outpatient protocol at 3 and 6 months. At all the appointments they will perform a standard hospital based 6MWT, which will again document resting heart rate and oxygen saturations, the distance the participant walks in 6 minutes and their heart rate and oxygen saturations at the end. Participants will be asked to use the app while performing the test. The BORG questionnaire will be also presented at the end of the test.

After the test, if no home 6MWT was performed within 3 days before the visit, participants will be reminded to perform a home test within the following 3 days. In addition, participants will be reminded to perform 6MWTs at home once per week, or at least once per month. At the end of the study, all participants will be asked to complete a usability and technology acceptance questionnaire and a group of randomly chosen 5 to 10 patients will be asked to attend a short interview about the use of the app.

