10.2. Number of Participants

This is an exploratory observational study and therefore no sample size calculation is provided, we propose collecting data on 30 participants.

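### O5 compares app and hospital change only in participants who start a therapy; with no reference from participants on unchanged therapy, unequal drift in the two methods cannot be separated from responsiveness

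*Combined protocol and SAP*

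**What the plan says.** Section 4 gives the tertiary objective as "To test whether the 6MWT app can detect changes in 6MWT distance more effectively than the hospital 6MWT, in patients starting advanced therapies". Its outcome measure is "Comparison of change in 6MWT app measurement with hospital 6MWT measurement, measured before and after initiation of new therapies". Section 10.3 (O5) adds that descriptive statistics on distance, saturation, heart rate, Borg score and steps "will be used to compare changes before and after initiation of new therapies".

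Neither section names a reference group, a practice walk, a repeated pre-therapy baseline or an adjustment for time. The general statement in 10.3 that all participants' data are used does not supply a reference, because a participant who starts nothing has no before and after initiation. Nor does O5 say which app reading it means. By contrast, O3 in the same section specifies a home reading close in time to the hospital visit.

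On exposure, section 5 plans hospital walks at baseline, 3 and 6 months, with the app run in indoor mode during the same walk. Home walks are preferably outdoors and are requested "preferably once per week and at least each month"; section 7.5 repeats this for follow-up ("participants will be reminded to perform 6MWTs at home once per week, or at least once per month"). This schedule applies to all participants, whether or not they start a therapy. On numbers, section 10.2 states that "no sample size calculation is provided, we propose collecting data on 30 participants"; how many will start a therapy is not given.

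**The concern.** To say that one method detects change better, one must know how much that method moves when nothing has been changed. Distance can drift without any drug effect, through familiarity with the test or the phone, a regular walking habit, season, or the course of the disease. Section 3 itself lists unfamiliarity with the environment and anxiety among the influences on the hospital walk.

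If home and hospital walks drift by different amounts, the gap between them in therapy starters mixes responsiveness with drift, and O5 could favour either method for reasons unrelated to therapy. Participants with unchanged therapy are followed with both methods on the same schedule, so their walk data could show the drift, but O5 does not use them.

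**Working it through.** The plan gives no effect size, SD, drift or number of starters for O5, so it has no figure to reproduce. The check is structural, with assumed values marked as such.

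**Structure.** For method m, let T_m be the therapy effect as that method registers it and d_m the drift over the interval. The observed before/after change is T_m + d_m. The method comparison is therefore

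app change − hospital change = (T_app − T_hosp) + (d_app − d_hosp).

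The first bracket is what O5 wants. The second is zero when drift is shared.

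**Can drift differ?** That depends on the app reading.
- Indoor-mode reading during the hospital walk: both methods measure the same walk, so drift in walked distance is common and cancels.
- Home walk: by the 3-month visit a participant has done 1 earlier hospital walk and about 3 (monthly) to 13 (weekly) home walks. By 6 months the counts are 2 and about 6 to 26. Setting and measurement also differ: outdoor GPS against a hospital corridor. Unequal drift is possible here.

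**Illustration.** Assumed SD of change 50 m, with the same true therapy effect T in both methods. Standardised response = (T + d)/50.

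| T (m) | d_app (m) | d_hosp (m) | App | Hospital | Without drift |
|---|---|---|---|---|---|
| 0 | 10 | 10 | 10/50 = 0.20 | 10/50 = 0.20 | 0 |
| 0 | 20 | 5 | 20/50 = 0.40 | 5/50 = 0.10 | 0 |
| 0 | 5 | 20 | 5/50 = 0.10 | 20/50 = 0.40 | 0 |
| 20 | 20 | 5 | 40/50 = 0.80 | 25/50 = 0.50 | 0.40 |

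Equal drift (row 1) leaves the comparison at zero, although each method shows a false 10 m change. Unequal drift produces a 15 m gap in either direction. Decline acts the same way: d_app = 0 and d_hosp = −15 also gives 0 − (−15) = 15 m.

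**What a reference adds.** If stable participants drift as starters do, starters minus stable is (T_m + d_m) − d_m = T_m for each method. In row 2 this gives 20 − 20 = 0 m for the app and 5 − 5 = 0 m for the hospital walk.

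**Precision.** 95% half-width for one method's change, with k starters of 30 (k assumed, SD 50 m):
- Starters only: t(k−1) × 50/√k.
- Starters minus stable: t(28) × 50 × √(1/k + 1/(30−k)).

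| Starters / stable | Starters only (m) | Starters minus stable (m) |
|---|---|---|
| 5 / 25 | 62 | 50 |
| 10 / 20 | 36 | 40 |
| 15 / 15 | 28 | 37 |

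At 10/20, an SD of 30 to 70 m gives 24 to 56 m for the contrast. Each of these half-widths is wider than the illustrative 15 m gap. The precision of the app-minus-hospital difference itself also depends on how the two changes correlate within a patient, which the documents do not give.

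**The case against.** The strongest reply is that O5 already has a concurrent comparator. The hospital walk is done by the same patients over the same period, and the question is about method, not about the size of the therapy effect. This stands: shared drift cancels, and what is missing is only a group with unchanged therapy.

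A reader might set an assumed drift of 10 to 30 m against the 42 m threshold in section 3 and take 10/42 = 24% to 30/42 = 71% as the bias. The documents do not support that. The range is assumed and one-sided, although section 3 calls the disease progressive. It also describes each method's own change, whereas only the difference in drift enters the comparison.

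Unequal drift is likewise conditional. It arises mainly if O5 uses home walks, and the plan does not say so. The 6MWT is already done at every outpatient appointment (section 5), so many participants may know the hospital test, and fitness gained at home could carry over to the hospital walk. Since O5 does not define what counts as more effective, a larger mean change need not count as better.

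The reference is also imperfect. Patients may start therapy because they are worsening, so decline and regression to the mean can differ between the groups. This stands too, and it is why starters minus stable should not replace the planned comparison.

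Finally, a reader might infer from sections 7.4 and 7.5 that therapy dates go unrecorded. The CRF is not among the documents and the flow chart is not shown, so that cannot be concluded.

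**Conclusion.** The point holds in a limited form. As written, O5 has no reference from participants with unchanged therapy, so it cannot separate a difference in responsiveness from a difference in drift. The problem is possible rather than shown: it depends on O5 using home walks and on the two series drifting unequally, and neither the size nor the direction of drift is documented. The 15 m gap above illustrates the mechanism; it does not estimate the bias.

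Priority is low and the change is optional. O5 is a tertiary, descriptive objective in a study that declares itself exploratory, and section 10.3 rests the study's success on the two O1 percentages, which this does not touch. The gain is that O5 would come closer to answering its own question with walk data already being collected.

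**What to change.** In section 10.3 (O5):
- Name the app reading used: the home walk, with its time window around the visit, or the indoor reading taken during the hospital walk.
- Alongside the starters' results, report the same app and hospital changes (mean, SD, confidence interval) from baseline to 3 months and from 3 to 6 months in participants with no therapy change in that interval.
- Show starters minus stable for each method as a supportive descriptive contrast, not as the basis of the comparison.
- Make sure therapy start and change dates are available to classify each interval, and state how starts that fall mid-interval, and the interval after a start, are handled.

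The cost is SAP wording, a little more analysis and, if the dates are not already captured, one CRF line per visit. No extra visit, walk or participant is needed. The drawback is a small, non-randomised reference group that may differ clinically from the starters, so the result stays descriptive.
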